4. STATISTICAL ANALYSES

4.1. General Considerations

4.1.1. General Methodology

The Safety analysis set will be used for all study population analyses and safety analyses, unless otherwise specified. The PK analysis set will be used for PK analyses. Study population and safety tables will be displayed overall and by dose level.

Confidence intervals will use 95% confidence levels unless otherwise specified.

Unless otherwise specified, continuous data will be summarized using descriptive statistics: n, mean, standard deviation, median, minimum and maximum. Categorical data will be summarized as the number and percentage of participants in each category.

4.1.2. Baseline Definition

For all endpoints (except as noted in baseline definitions) the baseline value will be the latest pre-dose of GSK3511294 assessment with a non-missing value, including those from unscheduled visits. If time is not collected, Day 1 assessments are assumed to be taken prior to first dose and used as baseline.

For ECG and/or Vital Signs analyses, if the latest, non-missing pre-dose values is from triplicate, the subject level baseline is defined as the mean of triplicate baseline assessments.

Unless otherwise stated, if baseline data is missing no derivation will be performed and baseline will be set to missing.

4.2. Primary Endpoint(s) Analyses

The pharmacokinetic (PK) analyses will be based on the Pharmacokinetic Population, unless otherwise specified.

4.2.1. Definition of Endpoint

4.2.1.1. Raw Plasma PK Concentrations

GSK3511294 plasma concentration-time data will be listed by dose level, study day, and nominal time.

4.2.1.2. Derived Plasma Pharmacokinetic Parameters

For each participant and for each dose, pharmacokinetic parameters described in Table 1 will be determined from GSK3511294 plasma concentration-time data, as data permit.

Table 1 Derived Pharmacokinetic Parameters

Parameter	Parameter Description
------------------	------------------------------

AUC(0-∞)	Area under the plasma concentration-time curve from time zero extrapolated to infinity will be calculated as: $AUC(0-inf) = AUC(0-t) + C(t) / \lambda_z$
AUC(0-t)	Area under the plasma concentration-time curve from time zero to the time of the last quantifiable concentration (C(t)) will be calculated using the linear trapezoidal rule for each incremental trapezoid and the log trapezoidal rule for each decremental trapezoid.
AUC(0-WeekX)	Area under the plasma concentration-time curve from zero to Week X will be calculated using the linear trapezoidal rule for each incremental trapezoid and the log trapezoidal rule for each decremental trapezoid. Planned parameters are AUC(0-Week4), AUC(0-Week12) and AUC(0-Week26).
%AUCex	The percentage of AUC (0-∞) obtained by extrapolation (%AUCex) will be calculated as: $[AUC(0-inf) - AUC(0-t)] / AUC(0-inf) \times 100$
C _{max}	Maximum observed plasma concentration, determined directly from the plasma concentration-time data.
t _{max}	Time to reach C _{max} , determined directly from the plasma concentration-time data.
t _{last}	Last time point where the concentration is above the limit of quantification.
CL/F	Apparent clearance $CL/F = \text{dose} / AUC(0-inf)$
V _z /F	Apparent volume of distribution.
λ _z	Terminal phase elimination rate constant. The number of points used to determine λ _z will also be reported.
t _{1/2}	Apparent terminal phase half-life will be calculated as: $t_{1/2} = \ln 2 / \lambda_z$

NOTES: Additional parameters may be included as required.

4.2.2. Main analytical approach

Plasma concentrations of GSK3511294 will be listed and summary statistics, including arithmetic mean, median, and standard deviations per GSK PK Display Standards, will be summarised by

dose and nominal time. Individual concentration-time profiles and median/mean profiles by GSK3511294 dose will be plotted on both linear and semi-logarithmic scale. Full details will be provided in the OPS.

Pharmacokinetic analysis will be the responsibility of the Clinical Pharmacology Modeling and Simulation Department, GSK. Plasma concentration-time data for GSK3511294 will be analysed by non-compartmental methods according to current working practices and using the currently supported version of WinNonlin version 8.0 (or higher). Calculations will be based on the actual sampling times recorded during the study.

All derived PK parameters will be listed. For each of these parameters, except T_{max} and T_{last}, the following summary statistics will be calculated for each dose level: median, minimum, maximum, arithmetic mean, 95% CI for the arithmetic mean, standard deviation, coefficient of variation ($\%CV = 100 * (\sqrt{\exp(SD^2) - 1})$) (where SD = SD of natural log transformed data), geometric mean and 95% confidence interval for geometric mean. For T_{max} and T_{last}, median, minimum, maximum, arithmetic mean, 95% CI, and standard deviation will be calculated. The first point, last point and number of points used in the determination of λ_z will be included on the listing of the derived parameters.

4.3. Secondary Endpoints Analyses

The secondary endpoints analyses including safety analyses and immunogenicity analyses. The safety and immunogenicity analyses will be based on the Safety Analysis Set, unless otherwise specified.

4.3.1. AEs and SAEs

4.3.1.1. Definition of endpoint(s)

The definitions of an AE or Serious Adverse Event (SAE) can be found in Appendix 3 of the Protocol.

4.3.1.2. Adverse Event Analyses

Adverse events analyses including the analysis of AEs, SAEs, and other significant AEs will be based on GSK Core Data Standards. AEs will be coded using the standard MedDRA and grouped by system organ class.

A table will be provided with a high-level summary of the subject incidence of any AEs, on-treatment AEs, drug-related AEs, AEs leading to study withdrawal, any SAEs, on-treatment SAEs, drug-related SAEs, fatal SAEs and drug-related fatal SAEs.

Subject incidence of all on-treatment AEs, drug-related AEs, and AEs leading to study withdrawal will be tabulated by system organ class and preferred term in descending order of frequency.

Summaries of on-treatment AEs by system organ class, preferred term and maximum intensity.

Subject incidence and occurrence of common ($\geq 5\%$) non-serious on-treatment AEs and serious on-treatment AE will be tabulated by system organ class and preferred term in descending order of frequency.

Summaries of non-serious drug-related AEs by preferred term in any dose cohort will be provided in descending order of frequency.

All AEs will be listed.

4.3.1.3. Adverse Events of Special Interest (AESI)

A summary table showing the number and percent of subjects, broken down by preferred term will be created using Hypersensitivity SMQ (narrow), Anaphylactic Reaction SMQ (narrow) and Vasculitis SMQ (narrow) as well as the number and percent of subjects with events of injection site reaction broken down by preferred term using MedDRA high level term (HLT) “Injection site reactions” under General disorders and administration site conditions SOC.

In addition, a profile summary table will be produced containing information including, but not limited to, the number of occurrences of the event, event characteristics, time to onset, intensity, outcome and whether it led to withdrawal from the study.

A listing will be produced for subjects reporting events under the specified above SMQs and MedDRA HLT.

4.3.1.4. COVID-19 Assessment and COVID-19 AEs

Number of participants with suspected, probable or confirmed for COVID-19 infection will be summarized according to the “COVID-19 Coronavirus Infection Diagnosis” and “COVID-19 Coronavirus Infection Assessment” eCRF page.

4.3.2. Laboratory Data

The hematology, clinical chemistry, urinalysis and additional parameters to be tested are listed in Appendix 2 of the Protocol.

Change from baseline for Chemistry and Hematology will be summarized.

Change from baseline for laboratory values will also be summarized by visit and worst-case post-baseline using categories of “To Low”, “To Normal or No Change” or “To High”. The derivation rule follows:

- Laboratory values will be classified as “Low”, “Normal”, or “High” based on the provided normal ranges.
- Change from baseline values will be classified relative to normal range as “To Low”, “To Normal or No Change”, or “To High”. Participants who do not change categories or move from out-of-range to normal will be classified as “To Normal or No Change”.
- A “worst case post-baseline” change classification will be derived for each treatment in which participants will be counted in the “To Low” or “To High” categories if they reported a change from a “Normal” baseline to a value below or above the normal range, respectively, at any on-treatment scheduled, unscheduled, or early withdrawal visits.

Participants who did not report a change to a value outside the normal range at any visit will be counted in the “To Normal or No Change” category.

- Participants having both high and low values relative to normal ranges at post-baseline on-treatment visits for safety parameters will be counted in both the high and low categories of the “worst-case post-baseline” row of related summary tables.

Urinalysis results will be summarized.

The criteria for potential clinical importance refer to section [6.2.1.1](#).

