
 
Report the event to GSK within 24 hours
 
Complete the liver event form, and complete an SAE data collection tool if the event also meets the criteria for an SAE
 
Perform liver chemistry event follow up assessments as described in the Follow Up Assessment column.
 
Monitor the participant until liver chemistries resolve, stabilise, or return to within baseline (see MONITORING )
 
 
MONITORING:
 
If ALT<math>\geq</math>3xULN AND total bilirubin <math>\geq</math> 2xULN or INR >1.5:
 
 
Repeat liver chemistries (include ALT, AST, alkaline phosphatase, total bilirubin and INR) and perform liver event follow up assessments within 24 hours
 
Monitor participant twice weekly until liver chemistries resolve, stabilise or return to within baseline
 
A specialist or hepatology consultation is recommended
 
	
 
Viral hepatitis serology
 
Obtain INR and recheck with each liver chemistry assessment until the aminotransferases values show downward trend
 
Obtain blood sample for pharmacokinetic (PK) analysis, obtained within a week of meeting increased liver monitoring criteria
 
Obtain serum creatine phosphokinase (CPK), lactate dehydrogenase (LDH), gamma-glutamyl transferase (GGT), glutamate dehydrogenase (GLDH) and serum albumin.
 
Fractionate bilirubin, if total bilirubin <math>\geq</math>2xULN
 
Obtain complete blood count with differential to assess eosinophilia. Note: The mechanism of action of GSK3511294 leads to lowering of eosinophils.
 
Record the appearance or worsening of clinical symptoms of liver injury, or hypersensitivity, on the liver event form
 
Record use of concomitant medications on the concomitant medications CRF page including acetaminophen, herbal remedies, recreational drugs and other over the counter medications.
 

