4.3.4. Vital Signs

Change from baseline for vital signs of Systolic Blood Pressure, Diastolic Blood Pressure, Heart Rate, Temperature, and Respiration Rate will be summarized.

Change from baseline for vital signs values of Systolic Blood Pressure, Diastolic Blood Pressure, and Heart Rate will also be summarized by worst-case post-baseline using categories of “To Low”, “To Normal or No Change”, or “To High”. The derivation rule is similar to Laboratory Data (section [4.3.2](#)) except the classification is based on the following potential clinical importance specified in section [6.2.1.3](#).

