6.2.5. Multiple measurements at One Analysis Time Point

Mean of the measurements (e.g., ECG) will be calculated and used in any derivation of summary statistics but if listed, all data will be presented.

If there are two values within a time window the value closest to the target day for that window will be used. If values are the same distance from the target, then the mean will be taken.

Participants having both High and Low values for Normal Ranges at any post-baseline visit (including post-baseline unscheduled assessments) for safety parameters will be counted in both the High and Low categories of “Any visit post-baseline” row of related summary tables. This will also be applicable to relevant Potential Clinical Importance summary tables.

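### The worst-case laboratory shift row leaves some High-to-Low and Low-to-High changes in no category and counts others in both directions

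*SAP*

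**What the plan says.** SAP 4.3.2 defines one shift table with two kinds of row and three categories (To Low, To Normal or No Change, To High). It introduces the table with "Change from baseline for laboratory values will also be summarized by visit and worst-case post-baseline using categories of". Four statements in that section decide who goes where.

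- **Second bullet (general rule, governing the by-visit rows).** "Participants who do not change categories or move from out-of-range to normal will be classified as"; the category named there is To Normal or No Change. There is no condition on baseline, so by implication High to Low is To Low and Low to High is To High.
- **Third bullet (worst-case row, shifts).** Participants are To Low or To High "if they reported a change from a “Normal” baseline to a value below or above the normal range, respectively". Scheduled, unscheduled and early withdrawal visits on treatment all count.
- **Third bullet (worst-case row, remainder).** "Participants who did not report a change to a value outside the normal range at any visit will be counted in the"; the category named is again To Normal or No Change.
- **Fourth bullet.** "Participants having both high and low values relative to normal ranges at post-baseline on-treatment visits for safety parameters will be counted in both"; this means both shift categories of the worst-case row, whatever the baseline. SAP 6.2.5 repeats this without a baseline condition.

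For vital signs, SAP 4.3.4 says "The derivation rule is similar to Laboratory Data", with limits of potential clinical importance in place of normal ranges. SAP 4.3.5 does the same for ECG.

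**The concern.** A worst-case row should show at least every participant that any single-visit row shows. Here the two kinds of row follow different rules. The by-visit rule accepts a shift from any baseline, while the worst-case rule accepts one only from Normal. The remainder category does not pick up the difference, because it is closed to anyone who changed to an out-of-range value.

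Two errors could follow. A participant who crosses the whole normal range may drop out of the worst-case row, so that the row no longer adds up to the cohort. Alternatively, a programmer who notices the gap may close it by default with To Normal or No Change, and a range-crossing change is then reported as no change. In a cohort of 10, either error moves a percentage by 10 points.

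The situation can arise. Protocol 5.1, criterion 2, lets the investigator admit participants with out-of-range laboratory values that the eligibility criteria do not list. For one haematology parameter a fall is expected: according to Protocol Appendix 5, "The mechanism of action of GSK3511294 leads to lowering of eosinophils".

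**Working it through.** The plan states no figure for this rule, so there is none to reproduce. The check is a full enumeration of the rule as written.

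**Inputs.** Baseline is Low, Normal or High (3 states). The set of categories seen after dosing is any non-empty subset of those three: 2³ − 1 = 7. Patterns: 3 × 7 = 21. The rules are the third bullet, its remainder sentence and the fourth bullet of SAP 4.3.2.

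**Cross-range patterns.** With a High baseline, 4 of the 7 subsets contain Low; with a Low baseline, 4 contain High. That makes 8 patterns.

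| Baseline | Categories seen after dosing | Worst-case row as written | With the fix below |
|---|---|---|---|
| High | Low | none | To Low |
| High | Low, Normal | none | To Low |
| High | Low, High | To Low and To High | To Low |
| High | Low, Normal, High | To Low and To High | To Low |
| Low | High | none | To High |
| Low | High, Normal | none | To High |
| Low | High, Low | To High and To Low | To High |
| Low | High, Normal, Low | To High and To Low | To High |

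As written, 4 patterns have no category and 4 are counted in both directions. The remaining 21 − 8 = 13 patterns are classified the same way before and after the fix. Without the fourth bullet, all 8 would be unclassified.

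**Illustration.** Take a cohort of 10. One participant is High at baseline, Low at Week 4 and Normal at every other visit; the other nine are Normal throughout.

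- Week 4 row: To Low 1/10 = 10%.
- Worst-case row: To Low 0/10, To High 0/10, To Normal or No Change 9/10. The row totals 90%.

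If that participant also had one High value after dosing, the worst-case row would show To Low 1/10 and To High 1/10, although the participant was already High at baseline.

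**Frequency.** The documents give no crossing rate. Assume a probability q per participant per analyte of any cross-range change, so that both the unclassified and the double-counted kinds are included. The chance of at least one such participant is 1 − (1 − q)^N. N is 20 as planned, or at most 20 + 2 × 6 = 32 with the additional recruitment in SAP 5.

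| q (assumed) | N = 20 | N = 32 |
|---|---|---|
| 0.1% | 2.0% | 3.2% |
| 0.5% | 9.5% | 14.8% |
| 1% | 18.2% | 27.5% |
| 2% | 33.2% | 47.6% |

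This range shows only how the answer depends on q. Nothing in the documents says where in the range, or outside it, the truth lies.

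**Vital signs and ECG.** In SAP 6.2.1.2, QTcF and QT have no lower limit, so neither can cross. PR would have to move between below 110 and above 220 msec. In SAP 6.2.1.3, systolic pressure would have to move between below 85 and above 160 mmHg, and heart rate between below 40 and above 110 bpm. SAP 4.3.4 and 4.3.5 use these categories for the worst case only, so there is no by-visit row to conflict with.

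**The case against.** The strongest reply is that little is lost. The fourth bullet and SAP 6.2.5 already capture the true shift in half of the cross-range patterns. The by-visit rows show a crossing at any summarised visit, and change from baseline in chemistry and haematology is summarised numerically as well. The table is descriptive, with no hypothesis test. Almost all of this stands, and it limits the point to one row.

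Several stronger readings are tempting, and the documents do not support them.

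- *The safety table as a whole undercounts shifts.* Only the worst-case row is affected, and in 4 patterns it overcounts.
- *The eosinophil response would disappear.* Haematology is drawn at 11 post-dose visits in the Schedule of Activities, so a sustained fall would appear in the by-visit rows and the numeric summary. The case also needs an above-range baseline in healthy participants screened for parasites, a laboratory lower limit that counts can fall below, and no High value after dosing. The lower limit is not given; if it is zero, the case cannot occur.
- *The chance of an above-range baseline measures the problem.* With assumed rates of 2%, 5% or 10%, at least one of 20 participants starts above range with probability 33%, 64% or 88%, from 1 − (1 − p)^20. That is not the chance of then crossing to Low.
- *The largest shifts are dropped.* A category crossing is not a measure of size. A fall from Normal to very low may be larger, and it is counted.

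Two things survive the reply. First, SAP 6.2.4 displays only scheduled timepoints and uses one value per window. A crossing seen only at an unscheduled visit outside the windows would therefore be missing from the by-visit rows, and the worst-case row is the one meant to catch it. Second, the table of clinical concern ranges in SAP 6.2.1.1 has no eosinophil entry, so those flags are no backup for that parameter.

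**Conclusion.** The point holds, and it is minor. Read literally, SAP 4.3.2 gives no worst-case category to 4 of 21 patterns and counts another 4 in a direction already present at baseline. What separates the two groups is only whether a post-dose value stayed in, or returned to, the baseline category. The rule also disagrees with the by-visit rule in the same section.

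The enumeration rests on the text alone. The frequency rests on a crossing rate that the documents do not give; in healthy participants it is probably low. Each affected participant is 10 percentage points of a cohort of 10, or 5 points of 20. No endpoint analysis, sample size or test depends on this row. For vital signs and ECG the same wording carries over by reference but will rarely matter.

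**What to change.** In the third bullet of SAP 4.3.2, replace the Normal-baseline condition with a baseline not already in that category:

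- To Low: any on-treatment Low value with a Normal or High baseline.
- To High: any on-treatment High value with a Normal or Low baseline.
- To Normal or No Change: everyone else with a baseline and at least one on-treatment value.

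Put the same condition into the fourth bullet and into the normal-range shift counts in SAP 6.2.5. If only the third bullet is changed, a High-baseline participant with both Low and High values would be To Low under one bullet and both under the other. Counts of potential clinical importance that do not refer to baseline can stay as they are. Carry the wording to SAP 4.3.4 and 4.3.5 for consistency.

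All 21 patterns are then classified, and the worst-case row agrees with the by-visit rows. The cost is a few lines of SAP text and one condition in the program, with no new data.

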4.3.3. Complement (C3 and C4)

Test results for Complement (C3 and C4) will be included within the laboratory data transfer and summarised by parameter and visit and presented as a table and as a figure. The summary table will include baseline concentration, concentrations at each visit and ratio to baseline at each visit. Summary statistics to be presented are n, geometric mean, standard deviation (on log scale), median, minimum and maximum.

4.3.4. Vital Signs

Change from baseline for vital signs of Systolic Blood Pressure, Diastolic Blood Pressure, Heart Rate, Temperature, and Respiration Rate will be summarized.

Change from baseline for vital signs values of Systolic Blood Pressure, Diastolic Blood Pressure, and Heart Rate will also be summarized by worst-case post-baseline using categories of “To Low”, “To Normal or No Change”, or “To High”. The derivation rule is similar to Laboratory Data (section [4.3.2](#)) except the classification is based on the following potential clinical importance specified in section [6.2.1.3](#).

4.3.5. ECG

A summary of the change from baseline in each ECG parameter by visit will be provided. When triplicate ECG assessments are taken, mean of the measurement will be calculated first and summary statistics will be based on the calculated mean. This will apply to both baseline and post baseline assessments.

A summary of the number and percentage of subjects who had normal and abnormal ECG findings will be displayed by scheduled visits. When multiple ECGs were performed at the same planned timepoint, the worst-case finding will be summarized.

Change from baseline for ECG parameters will be summarized by worst-case post-baseline using categories of “To Low”, “To Normal or No Change”, or “To High”. The derivation rule is similar to Laboratory Data (section [4.3.2](#)) except the classification is based on the potential clinical importance specified in section [6.2.1.2](#).

The maximum post-baseline QTcF values will be summarized using the categories of:

- <450 msec
- 450 to 480 msec
- >480 to 500 msec

- >500 msec

The maximum post-baseline uncorrected QT interval values will be summarized using the categories of:

- ≤600 msec
- >600 msec

The maximum increase in post-baseline QTcF values relative to baseline will be summarized using the categories of:

- ≤30 msec
- >30 to 60 msec
- ≥60 msec

